In four randomized clinical trials in which multiple teeth were treated with SDF for dental caries in preschool children, school-age children, and elders, not a single unexpected adverse event was reported (Llodra et al. 2005; Chu et al., 2002; Tan et al., 2010; Liu et al., 2012). In the Llodra et al. study (2005), 3 out of 225 children treated with SDF had transient mildly painful white lesions on the gingival surface near the tooth treated. These lesions resolved without treatment in 48 hours when the children were re-examined. These transient effects, although mildly adverse, were not unexpected. In a recent study in the US, targeting 3-5 year old children in Head Start centers, 38% SDF or placebo was applied (Milgrom et al., 2018). Within 24 to 48 hours of treatment, trained staff contacted parent/caregivers by telephone about adverse events. The questions included: (1) Has your child required medical care since his/her dental visit in the last 48 hours? (2) Has your child been to an emergency room, medical doctor, nurse or health care provider? (3) Since receiving the solution on the teeth has your child experienced any of the following? Nausea, not eating, vomiting, difficulty swallowing or breathing, swelling around the lips or skin of the face, itchiness around the lips or skin of the face, hives or rash, stomach ache, or diarrhea. Eight adverse events were reported by parents, 4 in each group. Based on enrolled participants, the adverse event rate was 11.1% in the placebo group (exact 95% CI: 3.2 to 26.7%) and 13.3% in the 38% SDF group (exact 95% CI: 3.7 to 30.7%). Based on all contacted participants, the adverse event rate was 15.4% in the placebo group (exact 95% CI: 4.3 to 34.9%) and 16.0% in the 38% SDF group (exact 95% CI: 4.5 to 36.1%). There were no statistically significant differences by treatment. The type of adverse event, severity and relationship of the adverse event to the treatment condition are reported in the Tables 1 and 2 below. The majority of the adverse events were either diarrhea or stomach ache, mild in severity and all resolved within 2 days of reporting. At the follow-up visit 14 to 21 days after treatment, a dental provider performed a visual examination to detect gingival or soft tissue stomatitis or ulcerative lesions. No participant was identified at that point with gingival or soft tissue stomatitis or ulcerative lesions.

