7.3 Intermediate Visits

7.3.1 24- to 48-Hour Safety Contacts (± 8 hours)

All participants will be contacted 24- to 48-hours after the baseline and 6-month trial visits to inquire if any Adverse Events (AEs), Serious Adverse Events (SAEs), or Unanticipated Problems (UPs) have occurred. This could be via a phone call, email, text, etc., or in person, if possible. All events will be recorded and reported, and the child will be brought in for an unscheduled visit as required. Additionally, the four questions from the Family Survey which refer to treatment acceptability may be asked at this time.

7.3.2 24- to 48-Hour Safety Visits (± 8 hours)

In addition to the 24- to 48-hour safety contacts, a safety visit 24- to 48-hours following application of the trial drug/placebo will be available for each participant after the baseline and 6-month trial visits. An intraoral soft tissue examination, including examination of the gingiva, will be performed. The status of the intraoral soft tissues will be recorded, and children with an AE (e.g., gingival irritation), SAE, or UP will be monitored until resolution of the problem or referred for treatment, if necessary. Refer to Appendix E and the MOP for additional details.

7.3.3 1.5-, 4.5-, 7-Month Intermediate Contacts (± 10 days)

Intermediate contacts will occur approximately 1.5, 4.5, and 7 months post baseline, and will allow the trial team to ask brief questions to inquire if any AEs, SAEs, or UPs have occurred, in addition to administering the tooth pain questionnaire to determine if an unscheduled trial visit is necessary to

evaluate the child. Additionally, medical conditions may be updated at the 4.5 month intermediate contact in order to confirm eligibility for the second application of SDF/placebo at the 6 month visit. These contacts will occur by a variety of strategies, including via phone, email, online survey, etc. The contacts will help to enhance retention.

All AEs, SAEs, and UPs will be recorded and reported. Trial teeth that cause pain due to caries, pulpal exposure, mobility, signs of pulpal infection (abscess, fistula, swelling) will be exited from the trial and referred for appropriate care (**early exit strategy**), and will be considered treatment failures in the analysis of the efficacy outcome.

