Sample size for the 24-48 h post-treatment safety visit is justified based on the 95% upper bound for the difference in 'safety event' between SDF and control. Erythema and 'adverse event' rate in previous studies are around 10-15% in the controls. Thus, assuming no safety difference between the two groups, and events occurring in 15% of the participants, the study sample will produce an upper bound for the difference at most 4% above the observed difference. Sample size calculations were made using PASS 13.

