6.12.1. Adverse Events

All reported AEs will be coded using the Medical Dictionary for Regulatory Activities (MedDRA) and summarized by System Organ Class (SOC) and Preferred Term (PT).

Analyses of AEs will be performed for those events that are considered treatment emergent AEs (TEAE), where treatment emergent is defined as: any AE with onset after the administration of study drug (SDF or placebo).

An overall summary of AEs without SOC and PT will be presented with the number and percentage of participants by treatment with any of the following types of AEs:

- TEAE
- TEAE by severity (mild, moderate, severe, life-threatening, fatal)

- TEAE by relationship to study drug (unrelated, related; where unrelated includes not related and unlikely related, and related includes possibly related, probably related, related)
- Serious TEAE
- TEAE leading to study drug discontinuation
- TEAE leading to death

In addition to the overall summary, the number and percentage of participants by treatment for each of the TEAE categories above will be summarized by SOC and PT. In these summaries, each participant will contribute only once to the incidence rate based on the most related occurrence and most severe occurrence of the AE. This is true regardless of the number of occurrences.

Summaries of TEAEs by SOC and PT will also include total number of unique AE occurrences, where unique AE occurrences include all events, regardless of whether the same participant experiences the same AE multiple times. However, if the end of a first occurrence and the start of a subsequent occurrence overlap, or the end of a first occurrence indicates “ongoing”, then this would be counted as only one occurrence.

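### The SAP tabulates adverse events only over the whole period after first administration, so the 24–48 hour window on which the protocol sized its safety visit has no planned SDF–placebo summary

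*SAP*

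**What the plan says.** **Definition and counting.** SAP 6.12.1 analyses treatment-emergent events, defined as "any AE with onset after the administration of study drug (SDF or placebo"). No end of window is given and no split by application. For the incidence tables, "each participant will contribute only once to the incidence rate based on the most related occurrence and most severe occurrence of the AE". The same section adds two further views: "Summaries of TEAEs by SOC and PT will also include total number of unique AE occurrences", and a breakdown described as "TEAE by relationship to study drug". SAP 6.3.3 has all eCRF data listed, with study day as a sort key. SAP 6.3.5 counts study day from the first application.

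**What the protocol collects and sizes.** Protocol 7.3.1: "All participants will be contacted 24- to 48-hours after the baseline and 6-month trial visits". Protocol 7.3.2 also makes an in-person soft tissue examination available in the same period after each application. Protocol 12.2: "Sample size for the 24-48 h post-treatment safety visit is justified based on the 95% upper bound" for the SDF–control difference, taking a 15% event rate and stating a bound at most 4 points above the observed difference.

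**What the protocol expects.** The reactions described in Protocol 2.2 are short-lived. In one cited trial, 3 of 225 treated children had mildly painful white gingival lesions: "These lesions resolved without treatment in 48 hours when the children were re-examined". In the US preschool trial, parents were telephoned within 24 to 48 hours. Most of the events they reported were diarrhea or stomach ache, and all resolved within 2 days of reporting.

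**The concern.** The trial builds its safety data collection around two short periods, and the SAP then has no table that looks at either of them. Gastrointestinal and allergic symptoms are asked about at every trial visit and interim contact (Protocol 8.1.2), and adverse events are captured until 7 days after the last day of participation (SAP 3.4). Two 48-hour periods are 4 days out of the 221–262 days to the 8-month visit, or 1.5–1.8% of follow-up. In the incidence percentages, a child with an ordinary stomach illness in month 4 and a child who vomits within hours of treatment fall in the same cell. A child who has had the event once cannot raise the percentage again after the second application.

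At stake is how clearly the report can say whether SDF causes more short-term reactions than placebo, and whether the second application differs from the first in that respect.

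**Working it through.** **1. The protocol's own figure.** Inputs from Protocol 12.2 and 5.4: 1,144 children allocated 1:1, so 572 per arm; event rate 15% in both arms; 10% attrition, so about 515 per arm.

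Margin = z × √(2 × 0.15 × 0.85 / n)

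- One-sided 95%, n = 572: 1.645 × √(0.255/572) = 3.47 points
- One-sided 95%, n = 515: 1.645 × √(0.255/515) = 3.66 points
- Two-sided 95%, n = 572: 1.96 × √(0.255/572) = 4.14 points

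The stated figure of at most 4 points is reproduced as a one-sided bound, even after attrition. It describes a 24–48 hour endpoint.

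**2. Is that endpoint tabulated?** SAP 6.12.1 has no window. Protocol 12.4 compares adverse events over the follow-up period, also without one. SAP 9 records that formal testing of adverse events was removed and says nothing of the 24–48 hour endpoint. The precision computed in Protocol 12.2 therefore belongs to no planned table.

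**3. What pooling does to an acute difference.** Let p be the risk in the acute window and b the risk of the same event at other times, assumed equal in both arms and independent of p.

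P(ever) = 1 − (1 − p)(1 − b), so the difference becomes (1 − b) × (p_SDF − p_placebo).

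Illustration: p_placebo = 15% (the protocol's sizing rate), p_SDF = 20% (assumed), 572 per arm, b assumed. Half-width = 1.96 × √[(c(1 − c) + t(1 − t))/572], with c and t the two arm risks.

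| b | Placebo | SDF | Difference (points) | 95% half-width (points) |
|---|---|---|---|---|
| window only | 15.0% | 20.0% | 5.0 | 4.4 |
| 10% | 23.5% | 28.0% | 4.5 | 5.1 |
| 30% | 40.5% | 44.0% | 3.5 | 5.7 |
| 50% | 57.5% | 60.0% | 2.5 | 5.7 |
| 70% | 74.5% | 76.0% | 1.5 | 5.0 |
| 90% | 91.5% | 92.0% | 0.5 | 3.2 |

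The ratio of difference to half-width falls at every step: 5.0/4.39 = 1.14 in the window, then 0.89, 0.61, 0.44, 0.30 and 0.16.

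**4. Excess at the second application only.** Assume 15% in both arms after the first application, and 15% against 20% after the second. A table for the second application shows 5.0 points. Counting each child once over both windows gives 1 − 0.85 × 0.85 = 27.75% against 1 − 0.85 × 0.80 = 32.0%, or 4.25 points. Multiplying by (1 − b) gives 2.97, 2.12 and 1.27 points at b = 30%, 50% and 70%.

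**5. Excess at both applications.** With 15% against 20% each time, the either-window difference is 0.85² − 0.80² = 8.25 points. The whole-study table would show 5.8, 4.1 or 2.5 points at b = 30%, 50% or 70%, with half-widths of 5.8, 5.5 and 4.7. The ratios are 1.00, 0.75 and 0.53, still below the 1.14 of a single-window table.

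**6. Low-background terms.** As b approaches 0 the factor (1 − b) approaches 1. For mucosal or skin staining, where b is plausibly near 0, the preferred-term table shows an acute difference almost undiluted.

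**The case against.** The other side has several sound points.

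- **Repeat events are not lost.** A reader might infer that reactions after the second application cannot be seen, or add nothing. The SAP does not support that. Unique occurrences are totalled by SOC and PT, so a repeat event counts unless the first was ongoing or overlapped it. Listings hold every event, and the number of applications is summarised (SAP 6.10). These totals, however, carry no timing and no per-application denominator. Placing an event after the second application means matching listings by hand, because study day runs from the first.
- **Relatedness rows use timing.** Protocol 9.3.1 includes temporal relationship among its criteria, so an illness in month 4 need not be graded as related. Protocol 5.4.2 masks the team and separates applier from examiner, and nothing in the documents shows biased grading. The rows remain case-by-case judgements, whereas a window compares the randomised arms directly.
- **The SAP did not drop a promised windowed analysis.** Protocol 12.4 was itself unwindowed. That leaves Protocol 12.4 and 12.2 unmatched.
- **An acute SDF excess is not established.** The one cited SDF–placebo comparison of parent-reported events had 4 in each group: 13.3% against 11.1% of those enrolled, and 16.0% against 15.4% of those contacted. The 5-point excess is only an illustration.
- **Labelling.** A reader might argue that the table is needed because a two-application indication is sought. Protocol 3.1 and 3.2.2 say the two-application outcomes are not intended for labelling claims, and the estimand in SAP 6.11.2 is a single application. The point does not rest on that argument.
- **Unseen shells.** Table shells are kept separately (SAP 11) and SAP 6 allows extra tables. The shells are to follow the SAP, which specifies no such table.

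**Conclusion.** The point holds as a gap in planned reporting. The one safety time point for which the protocol justified its sample has no planned summary by arm, and nothing planned compares the arms after each application.

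The size of the loss depends on the term. For vomiting, diarrhea, stomach ache and rash it is the factor (1 − b): a 5-point acute excess would read as 3.5 to 1.5 points for b between 30% and 70%, with a wider interval. For specific terms with little background it is small, so it would be wrong to infer that all acute reactions are buried. These figures assume independence between acute and background risk, equal background in the two arms, and values of b and of the excess that the documents do not supply. SAP 9 makes safety reporting descriptive, so the half-widths are a measure of precision and not the result of any planned test. Efficacy conclusions are unaffected. The change is worth making before the safety tables are produced.

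**What to change.** Add to SAP 6.12.1 descriptive tables by arm of any TEAE and of the solicited local, gastrointestinal and allergic symptoms, as follows:

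- **Window:** onset within a stated period matching the 24–48 hour contact and its 8-hour tolerance, that is up to 48 + 8 = 56 hours after application. Where only the onset date is known, use application day through day +2.
- **By application:** one table for the first application and one for the second.
- **Denominator:** the children who received that application, whether SDF or placebo.
- **Estimate:** SDF minus placebo risk difference with its 95% CI. At 15% in both arms the two-sided half-width would be about 4.1 points with 572 per arm and 4.4 points with 515.

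Keep the whole-study TEAE tables as the overall summary, and carry the new tables into the separate shell document.

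The cost is SAP wording, a few more tables and a rule for date-only onsets. The data are already collected, so no visit or treatment procedure changes. One limit remains: a contact can take place as early as 24 − 8 = 16 hours after application, so some later onsets inside the window will depend on recall at a subsequent contact. A footnote should say so.

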9.3.1 Relationship to Trial Intervention

The clinician’s assessment of an AE’s relationship to test article is part of the documentation process, but it is not a factor in determining what is or is not recorded in the trial database. If there is any doubt as to whether a clinical observation is an AE, the event should be recorded. All AEs will be recorded and reported periodically to the DSMB, NIDCR, and IND sponsor, and only those which meet the definition of an unanticipated problem will be reported to the SIRB within 5 days. All AEs must have their relationship to trial product assessed using the following terms:

1. Related (Possible, Probable, Related)
 - a. The event is known to occur with the trial intervention.
 - b. There is a temporal relationship between the intervention and event onset.
 - c. The event abates when the intervention is discontinued.

- d. The event reappears upon a re-challenge with the intervention.
- 2. Not Related (Unlikely, Not Related)
 - a. There is no temporal relationship between the intervention and event onset.
 - b. An alternate etiology has been established.

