Additional GLMs for binary and count outcomes and analysis of covariance models for continuous outcomes, as appropriate for each outcome above, will analyze the effects of covariates and their interactions with the treatment effect.

Aim 4 (Family-level outcomes): The P-CPQ, FIS, and satisfaction and acceptability scores will be compared between the SDF and placebo-treated groups using analysis of covariance, with trial site included as a covariate.

Additional analyses will consider the effects of covariates and their interactions with the treatment effect.

Changes in the color of treated lesions over time will be compared between treatments using a Cochran-Mantel-Haenszel chi-square test, with trial sites as the strata.

The family's experiences with ECC, child's brushing and dietary habits, and color change will be examined as additional covariates for the analyses of satisfaction and acceptability scores.

Safety: The proportion of infected trial teeth at each visit will be compared between the SDF and placebo-treated groups using a generalized estimating equation (GEE) model for binary outcomes, using an exchangeable correlation to account for possible non-independence among multiple teeth within a participant. Trial site will be included as a covariate.

The proportion of participants with adverse events (gum infection, oral mucositis, allergic reaction, anaphylaxis, nausea, vomiting, gastrointestinal pain, diarrhea; individually and the presence of any of the events) during the follow-up period will be compared between the SDF and placebo-treated groups using Cochran-Mantel-Haenszel chi-square tests, with trial sites as the strata.

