4. SAMPLE SIZE

The population will be children 12-71 months of age at the baseline caries examination attending early childhood education programs or recruited from clinics associated with the Michigan, Iowa or New York clinical trial sites.

The primary outcome of this trial is the proportion of arrested caries lesions approximately 6 months from the baseline visit (i.e., lesions that have changed from soft to hard over the trial period according to the ICDAS II activity criteria). A 10% difference in the proportion of arrested caries lesions between the SDF and placebo groups will be considered clinically significant. Prior studies in the literature of SDF using this outcome in primary cavitated lesions have shown a wide range for the proportion of arrested caries lesions for both SDF-treated and placebo-treated or untreated lesions; therefore the 10% difference in proportions was calculated assuming 55% versus 45% arrested caries lesions for SDF compared to placebo. In prior studies, an average of 4 lesions was treated per participant, with a within-participant correlation of 0.5; we are conservatively assuming 3 lesions per participant. The sample size calculations used a 2-sided test for a difference in proportions with cluster randomization (participant as the cluster) at significance level $\alpha=0.1\%$, with 80% power to detect a superiority difference of 10% for SDF compared to placebo. The calculations also account for the use of an early stopping rule for efficacy and futility. The interim analysis will be performed after approximately half of the sample has completed the 6-month examinations. A Lan-Demets spending function with an O'Brien-Fleming type boundary will be used, with p-values for efficacy at 0.000001709 and 0.00099938 at 50% and 100% completion, respectively. Non-binding p-values for stopping due to futility at 50% and 100% completion will be 0.2336928 and 0.00099938, respectively. With the above assumptions, the trial will require 1144 participants to be enrolled. Sample size calculations were made using East version 6.

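### The SAP's rule for merging adverse event records ignores the tooth, so concurrent infections in different trial teeth count as one occurrence

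*SAP*

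**What the plan says.** SAP 6.12.1 tabulates treatment-emergent events by system organ class and preferred term in two ways.

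- **Participant incidence:** "each participant will contribute only once to the incidence rate based on the most related occurrence and most severe occurrence of the AE".
- **Occurrences:** "unique AE occurrences include all events, regardless of whether the same participant experiences the same AE multiple times". Two situations are excepted, and in both the records are merged. The first is overlap in time: "if the end of a first occurrence and the start of a subsequent occurrence overlap". The second concerns an earlier record that was never closed: "or the end of a first occurrence indicates “ongoing”, then this would be counted as only one occurrence".

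The SAP does not define when two records are the same AE. It names no tooth and no application period in the merge rule, and sets no time limit on the 'ongoing' clause.

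The protocol treats infection by tooth. Section 12.4 plans a comparison of the proportion of infected trial teeth at each visit, using a GEE model "to account for possible non-independence among multiple teeth within a participant". SAP 6.12 contains no such summary, not even a descriptive one. SAP Section 9 records only that safety became descriptive and that formal testing of adverse events was removed.

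**The concern.** Tooth infection and toothache are listed harms in Protocol Appendix E, and both happen to a tooth. An abscess in a second tooth is a new event, not a continuation of the first. A preferred term cannot tell the two apart, so the merge rule joins them whenever their dates overlap or the first was never closed.

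Unclosed records are foreseeable. Under Protocol 7.3.3 an affected trial tooth is exited and referred. Under Protocol 9.1 and 9.2 follow-up of an event may end because it is considered stable or the child is lost to follow-up, so some events may never receive a resolution date. As written, such a record absorbs every later record with the same term in that child.

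At stake is one descriptive column. For infection, though, no other SAP safety table could show that a child had more than one infected tooth.

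**Working it through.** The documents give no figure for this point, so there is none to reproduce. The check has two parts.

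**1. Apply the rule to four simple histories of one preferred term in one child.**

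| History | Count under SAP 6.12.1 | Count by tooth and episode |
|---|---|---|
| Two teeth, days 40–60 and 50–70 | 1 | 2 |
| Two teeth, days 40–45 and 100–105 | 2 | 2 |
| Event resolved on day 3, repeat on day 183 after the second application | 2 | 2 |
| First event from day 40 'ongoing', new event on day 190 after the second application | 1 | 2 |

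The rule loses events in the first and fourth histories only. The child counts once for incidence in all four.

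**2. Bound the loss.**

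Inputs:

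- Teeth per child, m = 3, the planning value for lesions in SAP Section 4. That section also reports "an average of 4 lesions was treated per participant, with a within-participant correlation of 0.5" from prior studies, so m = 4 is shown as well. Lesions stand in for teeth.
- Correlation ρ from 0 to 0.5. The 0.5 is the SAP's value for lesion arrest, not for adverse events.
- Risk per tooth, p = 3–10%. This is an assumption; the documents give no such figure.
- Children per arm: 1144 / 2 = 572.

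Under a beta-binomial model with s = 1/ρ − 1 and b = (1 − p)s, the chance that a child has no affected tooth is P0 = product over i = 0 to m − 1 of (b + i)/(s + i). At ρ = 0 it is (1 − p)^m. If every multi-tooth episode collapses to one, the share of tooth events lost is L = 1 − (1 − P0)/(mp).

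Worked case, m = 3, p = 0.05, ρ = 0.5, so s = 1 and b = 0.95:

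- P0 = 0.95 × 1.95 × 2.95 / 6 = 0.9108
- Affected children: 572 × 0.0892 = 51.0
- Affected teeth: 572 × 3 × 0.05 = 85.8
- L = 1 − 51.0/85.8 = 41%

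| m = 3 | ρ = 0 | ρ = 0.5 |
|---|---|---|
| p = 3% | 1 − 0.0873/0.09 = 3% | 1 − 0.0541/0.09 = 40% |
| p = 5% | 1 − 0.1426/0.15 = 5% | 41% |
| p = 10% | 1 − 0.271/0.30 = 10% | 1 − 0.1735/0.30 = 42% |

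A second calibration sets the share of children with any event to 8–12%. That is the emergency-visit rate during the operating-room waiting period in Protocol 2.3.2, used here as a stand-in. With 3 teeth it gives 3–4% at ρ = 0 and 40–41% at ρ = 0.5. With 4 teeth it gives 3–5% and 49–50%.

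All these are ceilings. If only a fraction f of the excess teeth merge, the loss is f × L. In the worked case the excess is 85.8 − 51.0 = 34.8 teeth, and at f = 0.5 the loss is 17.4 of 85.8, or 20%.

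**The case against.** The strongest reply is that little depends on this column. No test uses it, participant incidence keeps the worst severity and closest relationship, and SAP 6.3.3 lists every eCRF record. All of that stands, and it limits the point to one descriptive count.

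A reader might infer more than the documents support:

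- **That recurrences after the second application are lost.** They are counted whenever the first event has ended. The lost case needs a record still open some six months later. For mucosal irritation the documents point the other way: Protocol 2.2 reports gingival lesions that resolved within 48 hours, and Protocol 7.3.2 provides for monitoring to resolution or referral.
- **That re-challenge evidence is destroyed.** Protocol 9.3.1 lists "The event reappears upon a re-challenge with the intervention" among the considerations in the clinician's judgement of each event. It is not read from a table total, and the column is not split by application in any case.
- **That toothache in several teeth goes unseen.** SAP 6.11.4 analyses pain by treated lesion at 3, 6 and 8 months, and SAP 6.11.5 sums verified episodes per child.
- **That the loss is 40% or more.** That requires every multi-tooth episode to merge and borrows a correlation from another outcome. SAP 6.11.5 itself speaks of few participants with any pain.

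Two further objections stand in part. The documents do not say that the AE form holds one record per tooth. If one record covers a child's whole episode, the merge rule removes nothing, although the column then cannot show several teeth either. And merging has a proper purpose: it stops one continuous event from being counted twice when it is recorded again at a later visit.

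**Conclusion.** The point holds in a limited form. The merge rule in SAP 6.12.1 takes no account of the tooth, so concurrent infections in different trial teeth, or a new-tooth infection during an unclosed earlier one, count once. This understates the only planned SAP safety summary that could show several infected teeth per child. Lesions exited for abscess or fistula do enter the primary analysis as failures (SAP 6.11.1), but there they are pooled with pain and other causes of non-arrest and do not give an infection count.

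The size is unknown. With 3 teeth and the assumed 3–10% risk per tooth, it is at most about 3–10% at zero correlation and 40–42% at 0.5. The actual loss depends on how often episodes overlap or stay open, and on whether AE records are kept by tooth. The documents settle neither. They also give no basis for saying how far any difference between the arms would be distorted. The correction is worth making because it is cheap and the rule is explicit, not because a conclusion of the trial turns on it.

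**What to change.** In SAP 6.12.1, define when two records are one occurrence:

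- For tooth-specific events (tooth infection, toothache), merge overlapping or ongoing records only if they share both the preferred term and the tooth.
- For other events, count a record with a distinct new onset after the second application as a new occurrence. A continuation of an unresolved event stays merged, so that a single event is not counted twice.
- Leave participant-level incidence as it is.

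This takes a sentence or two in the SAP and some programming. Occurrence counts may rise slightly. It also requires AE records to be linked to a tooth. SAP 6.11.1 already uses adverse events to derive lesion failures, so some linkage exists, but the sponsor should confirm that the tooth is recorded for every tooth-specific event.

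The merge fix does not restore the protocol's per-visit summary of infected trial teeth. The sponsor could add it to SAP 6.12 as a descriptive table, or list its removal explicitly in SAP Section 9.
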